5.3.2.3. Other Clinical Course Parameters

5.3.2.3.1. Respiratory Rate, Heart Rate, Oxygen Saturation and Body Temperature

Descriptive statistics will be shown for the actual values and changes from baseline by visit and by treatment group. Descriptive statistics will include the number of subjects, mean, standard deviation, standard error, 95% confidence interval, median, range and interquartile range.

Graphical presentation of the Mean±SE of both actual values and changes from baseline vital signs over time will be provided.

The aforementioned will be presented overall by treatment group and by the subgroups as defined in Section 2.4.

5.3.2.3.2. Hospitalized Subjects only

Time to Discharge, Time to Clinical Stability: Protocol Definition, Time to Clinical Stability: Investigator Assessment

These time to event variables will be analyzed using Kaplan-Meier analysis. Both the 80% and 95% 2-sided confidence intervals will be presented.

The aforementioned will be presented overall by treatment group and by the subgroups as defined in Section 2.4

In addition, for time (hours) to hospital discharge (relative to date/time of first dose of study drug), the differences in median time of active dosing regimens versus placebo treatment will also be estimated using the AFT model. The AFT model will include the categorical effects for treatment (with placebo as the reference) and randomization stratification factors (derived). A summary of information from the final AFT model will include parameter estimates and associated standard errors and covariance matrix of parameter estimates, estimated accelerated failure time ratios versus placebo and the associated 80% and 95% 2-sided confidence intervals will be presented.

The aforementioned will be presented overall by treatment group and by the subgroups as defined in Section 2.4.

The parameter estimates and associated variance matrix resulting from AFT model, will be used in a generalized MCP-Mod approach that will test for existence of dose-response, at alpha=0.10 (1-sided). The aforementioned MCP-Mod will be presented overall by treatment group only.

Graphical presentation will include:

- Overlay of survival curves with Kaplan-Meier survival function and AFT on one plot
- Forest plot of accelerated failure time ratios and resulting confidence intervals for subgroups of interest as defined in Section 2.4 including the relevant subgroup variable as covariate in the model with subgroup*treatment group interaction.

Association Between Time (hours) to Hospital Discharge and Covariates/Baseline Indicators

For Cohort 1 (hospitalized) subjects, the potential association between the time (hours) to hospital discharge (relative to date/time of first dose of study drug) and covariates/baseline indicators of interest, as detailed in Section 5.3.2.1, will be explored utilizing a similar AFT model as described above but including the relevant subgroup variable as covariate in the model with subgroup*treatment group interaction.

RSV-related Re-hospitalization

The proportion (number [n] and percentage [%]) of subjects will be presented as frequency tabulation:

- Re-hospitalized (any reason): percentage (%) based on total number of hospitalized subjects in ITT-i analysis set and treatment group
- Re-hospitalized:
 - Adverse event:
 - Respiratory AEs:
 - ◆ RSV-related complications: modified definition as detailed in Section 5.4
 - ◆ Other respiratory AEs
 - Non-respiratory AEs
 - Other

In addition, the main reason(s) for re-hospitalization will be summarized descriptively.

Individual subject profiles will be provided for all subjects re-hospitalized.

Time to Discharge Since Hospital Admission, Time to Clinical Stability: Investigator Assessment Since Hospital Admission

These time to event variables will be analyzed using Kaplan-Meier analysis. Both the 80% and 95% 2-sided confidence intervals will be presented.

The aforementioned will be presented overall by treatment group and by the subgroups as defined in Section 2.4.

Need for ICU Stay, Need for Oxygen Supplementation, Requirement for Supplemental Feeding/Hydration

With reference to the definitions and derivations detailed in Section 5.3.1.3.2, summary includes those subjects not requiring the level of care/support at date/time of first dose of study drug.

The proportion (number [n] and percentage [%]) of subjects with data available will be presented, as frequency tabulation, by treatment group. Additionally, 95% 2-sided confidence interval for each binomial proportion within the individual categories will be presented as based on the Wilson score test.

Based on the categorization (Yes vs No), the difference in proportions between each active treatment group as compared to placebo will be investigated. Frequency procedure in SAS® provides Newcombe confidence limits with Mantel-Haenszel weights for the common risk difference (difference in proportion), controlling for the two randomization stratification factors (separately). The difference in proportion of 'Yes' for any ICU/supplementation need and both 80% and 95% 2-sided confidence intervals for this point estimate, controlling for randomization stratification factors (derived), will be presented.

Derived duration will be summarized descriptively only.

The aforementioned will be presented overall by treatment group and by the subgroups as defined in Section 2.4.

Requirement for Non-invasive Non-mechanical Ventilation Support, Requirement for Non-invasive Mechanical Ventilation Support, Requirement for Invasive Mechanical Ventilation Support

These need for/requirement parameters will be summarized in similar manner as described above and will only be calculated for those subjects that do not require ICU stay or supplemental support (depending on the parameter of interest) before the first dose of study drug.

Time (hours) to End of Oxygen Supplementation, Time (hours) to End of Hydration/Feeding Supplementation, Time (hours) to End of Supplementation (up to 72h from first hospital discharge)

These time to event variables will be analyzed using Kaplan-Meier analysis. Both the 80% and 95% 2-sided confidence intervals will be presented.

The aforementioned will be presented overall by treatment group and by the subgroups as defined in Section 2.4.

In addition, time (hours) to end of oxygen supplementation (up to 72h from first hospital discharge), difference in median time (hours) to event between each active treatment group as compared to placebo will be investigated using the AFT model with log-logistic distribution. The model will include class variables treatment group with placebo as reference and randomization stratification factors (derived). Summary will include parameter estimates and associated standard error, covariance matrix of parameter estimates, estimated accelerated failure time ratio (as compared to placebo) and both 80% and 95% 2-sided confidence intervals.

The aforementioned will be presented overall by treatment group and by the subgroups as defined in Section 2.4.

Graphical presentation will include:

- Overlay of survival curves with Kaplan-Meier survival function and AFT on one plot

- Forest plot of accelerated failure time ratios and resulting confidence intervals for subgroups of interest as defined in Section 2.4 including the relevant subgroup variable as covariate in the model with subgroup*treatment group interaction.

Time to Return to Pre-RSV Disease Level for Respiratory Rate, Time to Return to Pre-RSV Disease Level for Heart Rate, Time to SpO2>92% on Room Air, Time to SpO2>95% on Room Air

These time to event variables will be analyzed using Kaplan-Meier analysis. Both the 80% and 95% 2-sided CIs will be presented.

The aforementioned will be presented overall by treatment group and by the subgroups as defined in Section 2.4.

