Each of the following risk factors for severe RSV disease (subcategories of the above):	
- prematurity at birth	
- bronchopulmonary dysplasia	
- congenital heart disease	
- Down syndrome	
- neuromuscular impairment	
- cystic fibrosis	
- recurrent wheezing/asthma	
- other congenital disease	
- other	
Receiving Supplemental Oxygen prior to first intake of study medication (no, yes)	
Prenatal Smoking by the subject's mother (no, yes)	
Exposed to tobacco smoke in home environment (no, yes)	
History of wheezing associated with acute respiratory infection (no, yes)	
History of atopic dermatitis (eczema) (no, yes)	
History of allergy (no, yes)	
If yes, type of allergy (allergic dermatitis, allergic rhinitis, allergic bronchitis, food allergy)	
History of asthma (no, yes)	
Contact with HCP before presenting (no, yes)	
If yes, type of HCP (General Practitioner, Pediatrician, Other)	
Breastfeeding (no, yes)	
Routinely attending daycare (no, yes)	
Received palivizumab (no, yes)	
Received aerosolized ribavirin (no, yes)	
Received IV immunoglobulin (no, yes)	
Presence of other respiratory pathogens (No vs Yes)	
Presence of other respiratory viruses (No vs Yes)	
Presence of respiratory bacteria (No vs Yes)	
Prior use of antitussives	
• No: No prior use	
• Yes: Any prior use	
Prior use of bronchodilators	
• No: No prior use within the 24h before first dose of study drug	
• Yes: Any prior use within the 24h before first dose of study drug	
Prior use of mucolytics	
• No: No prior use	
• Yes: Any prior use	
Prior use of inhaled corticosteroids	
• No: No prior use or use to a maximum of 2 consecutive days	
• Yes: Any prior use for a minimum of 3 consecutive days	
Prior use of systemic corticosteroids	
• No: No prior use or use to a maximum of 2 consecutive days	
• Yes: Any prior use for a minimum of 3 consecutive days	
Prior use of any medication of interest	
• No prior use	

Table 10: Baseline Characteristics

	Summary Type

 • Prior use of only one medication of interest • Prior use of 2 or more medications of interest 	

* Only nasal swab type samples to be considered.

Medications of interest: programmatically identified based on WHO-DD ATC codes and product names. List of medications to be finalized in collaboration with medical review prior to use in analyses. Refer to Section 4.6 for further details.

Duration of RSV symptoms prior to randomization will be calculated by considering:

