5.3.2. Endpoint-specific analysis methods

5.3.2.1. RSV RNA Viral Load (qRT-PCR)

Log₁₀ RSV RNA Viral Load

Descriptive statistics mean (SE) graphs and median (IQR) graphs will be shown for the log₁₀ RSV RNA viral load actual values and changes from baseline by analysis visit and by treatment group. Descriptive statistics will include the number of subjects, mean, standard deviation, standard error, 95% confidence interval, median, range and interquartile range. The aforementioned will be presented by the subgroups as defined in Section 2.4.

Differences on log₁₀ RSV RNA viral load by qRT-PCR between treatment groups and by analysis visit will be determined using appropriate contrasts in a similar mixed effects model as the one used for the primary efficacy endpoint (see Section 5.2.3). The 95% 2-sided confidence intervals will be presented.

Association Between Log₁₀ RSV RNA Viral Load and Covariates/Baseline Indicators

The potential association between the log₁₀ RSV RNA viral load and the following covariates and/or baseline indicators will be explored:

- Baseline log₁₀ RSV RNA viral load
- Presence/absence of risk factors for severe RSV disease
- Days since symptom onset (0,1,2,3,4,5)
- RSV subtype
- Medications of interest:
 - ◆ Any prior/concomitant use
 - ◆ No prior/concomitant use
- Supplemental oxygen at baseline
- Presence of other respiratory pathogens at baseline
- Presence of other respiratory viruses at baseline
- Age as collected at Screening (as continuous variable)
- Overall RSV symptoms summary score (ObsRO) at baseline
- Overall RSV symptoms summary score (ClinRO) at baseline
- Region [Class 2]
- Cohort [Class 1]
- Baseline neutrophils count (as continuous variable)

To predict the change in log₁₀ RSV RNA viral load over time at Day 3, Day 5 and Day 8 based on the aforementioned set of predictor variables (covariates and/or baseline indicators), multiple regression analysis using backward stepwise elimination, will be performed initially fitting all predictor variables to identify the prognostic factors. Then

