The potential association between the change from baseline in summary scores of the summary parameter, PRESORS ObsRO: key RSV symptoms and the covariates and/or baseline indicators of interest will be explored over time at Day X, Day 8 and Day 10 in a similar manner, utilizing multiple regression with backward stepwise elimination, as described for the RSV RNA viral load. Refer to Section [5.3.2.1](#) for details.

Day X is defined as the day when at least 50% of Cohort 1 subjects, across all treatment groups, have been discharged from hospital. The day identified will be used for both cohorts.

PRESORS ObsRO: Change from Baseline: Mixed Model Repeated Measures

For the summary parameter, PRESORS ObsRO: key RSV symptoms, change from baseline over time (average of the worst [primary approach] daily summary scores) will be analyzed using a restricted maximum likelihood based repeated measures approach. The analysis model will include fixed (discrete) effect parameters for treatment, randomization stratification factors (derived), analysis visit and treatment-by-analysis visit interaction, as well as continuous covariates for the baseline summary parameter score and baseline summary parameter score-by-analysis visit interaction. An unstructured covariance structure will be selected to model the within-subject errors. In case this model will not converge, the Toeplitz covariance structure will be applied. The Kenward-Roger approximation will be used to estimate the denominator degrees of freedom.

Differences between treatment groups and by analysis visit will be determined using appropriate contrasts. Both the 80% and 95% 2-sided confidence intervals will be presented.

For subgroup analyses, the model will also include the subgroup variable as a covariate and the subgroup-by-treatment, subgroup-by-analysis visit and subgroup-by-analysis visit-by-treatment interactions. For details about subgroups refer to Section [2.4](#).

Time to Resolution of Symptoms (Concepts) and Four Summary Parameters: Key RSV Symptoms, Respiratory Symptoms, General Illness Behavior and Overall RSV Symptoms (ObsRO)

For the RSV symptoms (concepts) and four summary parameters, these time to event variables will be analyzed using Kaplan-Meier analysis. Both the 80% and 95% 2-sided confidence intervals will be presented.

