The aforementioned will be presented overall by treatment group and by the subgroups as defined in Section 2.4, for summary parameters, key RSV symptoms and overall RSV symptoms only.

For time to resolution of summary parameters, key RSV symptoms and overall RSV symptoms (ObsRO), sensitivity analyses will be performed considering 4 different imputation methods:

- Method 1: from first resolution (score 0 or 1) after last unresolved value onwards, impute missing data as resolved.

- Method 2: impute all missing values as unresolved (score >1).
- Method 3: impute all missing values in-between resolved observations (score 0 or 1) as resolved.
- Method 4: impute all missing values as unresolved (score >1), except when in-between resolved values where resolved is imputed.

These sensitivity analyses will be provided from IA#3 onwards.

In addition, for the summary parameters, key RSV symptoms and overall RSV symptoms, difference in median time (hours) to resolution (event) between each active treatment group as compared to placebo will be investigated using the AFT model with log-logistic distribution. The model will include class variables treatment group with placebo as reference and randomization stratification factors (derived) and baseline summary parameter score. Summary will include parameter estimates and associated standard error, covariance matrix of parameter estimates, estimated accelerated failure time ratio (as compared to placebo) and both 80% and 95% 2-sided confidence intervals.

The aforementioned will be presented overall by treatment group and by the subgroups as defined in Section 2.4.

Parameter estimates and associated variance matrix resulting from AFT model, will be used in a generalized MCP-Mod approach to test dose-response, at 1-sided alpha level=0.10. The aforementioned MCP-Mod will be presented overall by treatment group only.

Graphical presentation will include:

- Overlay of survival curves with Kaplan-Meier survival function and AFT on one plot
- Forest plot of accelerated failure time ratios and resulting confidence intervals for subgroups of interest as defined in Section 2.4 including the relevant subgroup variable as covariate in the model with subgroup*treatment group interaction.

Status of RSV Symptoms, Status of Health, Status of Improvement of RSV Symptoms, Status of Return to Pre-RSV Disease Health (ObsRO)

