5.4.2. Analysis Methods

PRESORS ObsRO: RSV Recovery Scale (RRS): Day 1 to Day 8

The RRS will be assessed from Day 1 to Day 8. The proportion (number [n] and percentage [%]) of subjects per ordered categories will be presented, as frequency tabulation and graphically, by treatment group and study day.

The proportional odds model will be used to analyze the RRS Day 2 to Day 8, modeling the common odds ratio (cOR) of improvement on the ordinal scale of each active treatment group versus placebo. Ordered logistic regression model will include treatment group, baseline RRS category and the two randomization stratification factors (derived). The proportional odds model will be defined in such a way that a $\text{cOR} < 1$ indicates larger improvement in the active treatment group.

The aforementioned will be presented overall by treatment group and by the subgroups as defined in Section 2.4.

Resolved Status Based on PRESORS ObsRO/ClinRO: Day 1 to Day 8, Resolved Status Based on PRESORS ObsRO/ClinRO Before/After Hospital Discharge

Proportion (number [n] and percentage [%]) of subjects per individual categories will be presented graphically, by treatment group.

The aforementioned will be presented overall by treatment group and by the subgroups as defined in Section 2.4.

PRESORS ClinRO: Clinically Resolved Status: Day 1 to Day 8

Clinically resolved status, will be assessed from Day 1 to Day 8. The proportion (number [n] and percentage [%]) of subjects per individual categories will be presented, as frequency tabulation and graphically, by treatment group and study day.

A logistic regression model will be used to analyze the binary dependent variable, clinically resolved status Day 2 to Day 8, comparing each active treatment group versus placebo. Logistic regression model will include treatment group and the two randomization stratification factors (derived). Estimate of the treatment difference in proportion of clinically resolved status and both 80% and 95% 2-sided confidence intervals for this estimate will be obtained from the logistic regression model.

The aforementioned will be presented overall by treatment group and by the subgroups as defined in Section 2.4.

A sensitivity analysis will be performed applying the alternative imputed value (Column 4: Sensitivity analysis imputed value [Section 5.4.1]).

PRESORS ObsRO/ClinRO: Time to Resolution [Supplemental-free Definitions] and PRESORS ObsRO: Time to Resolution From Hospital Discharge

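### The models for time to hospital discharge and clinically resolved status omit baseline severity, which is collected and used in related models; the loss is precision, not validity

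*SAP*

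**What the plan says.** Three comparative models for hospitalized children contain only treatment and the two derived stratification factors:

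- Time to hospital discharge (Section 5.3.2.3.2): "The AFT model will include the categorical effects for treatment (with placebo as the reference) and randomization stratification factors (derived". The estimates and their variance matrix go into MCP-Mod at one-sided 10%.
- Time to end of oxygen supplementation (same section): "The model will include class variables treatment group with placebo as reference and randomization stratification factors (derived".
- Clinically resolved status, Day 2 to Day 8 (Section 5.4.2): "Logistic regression model will include treatment group and the two randomization stratification factors (derived".

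The stratification factors are time since symptom onset and presence of a risk factor for severe disease (Section 5.1). Neither measures current severity.

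Related models do adjust for baseline state. The caregiver-reported time-to-resolution model in Section 5.3.2.2 reads "The model will include class variables treatment group with placebo as reference and randomization stratification factors (derived) and baseline summary parameter score". The repeated-measures model in the same section has treatment, stratification factors and visit terms, "as well as continuous covariates for the baseline summary parameter score and baseline summary parameter score-by-analysis visit interaction". The time to confirmed undetectable virus model (Section 5.3.2.1) includes baseline viral load. The RSV Recovery Scale (RRS) model, also for Cohort 1 and in the same section as clinically resolved status, reads "Ordered logistic regression model will include treatment group, baseline RRS category and the two randomization stratification factors (derived".

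Baseline severity is available. Table 10 lists "Receiving Supplemental Oxygen prior to first intake of study medication (no, yes", and the baseline indicators in Section 5.3.2.1 include "Overall RSV symptoms summary score (ClinRO) at baseline".

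**The concern.** A child who needs oxygen or feeding support at first dose can be expected to leave hospital later, and to meet a composite of no oxygen, no feeding support, no ICU need and resolved symptoms later, than a child who does not. When such a predictor is left out, its variation stays in the error term and the 80% and 95% intervals are wider than they need be. Cohort 1 has about 48 children per arm, so there is little precision to spare.

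Clinically resolved status is worse placed. Sections 2.4 and 5.4 direct the exploratory endpoints in Cohort 1 to children with symptom onset of 3 days or less. Fewer than 48 per arm then remain. Symptom onset is also constant in that stratum, so risk factor is the only covariate still doing any work.

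**Working it through.** **The SAP's own Cohort 1 figure.** Section 1.4 gives a placebo median of 3 days, a 1-day reduction (2/3, stated as 66%), a scale parameter of 1/0.65, 48 per arm, and a 95% probability of an observed effect in the right direction.

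- For a log-logistic AFT model without covariates and σ = 0.65, SE(log time ratio) = √(2·3·σ²/n) = √(6 × 0.4225/48) = 0.230.
- |ln(2/3)| = 0.405, so Φ(0.405/0.230) = 96.1%.
- Simulated unadjusted fits (2,000 trials per scenario, censored at day 28) gave 95.0-96.3%.

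The figure reproduces with σ = 0.65. With σ = 1/0.65 = 1.54 the probability would be 77%. The figure concerns symptom resolution; it is used here only because it supplies the SAP's one Cohort 1 scale.

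**Size for time to discharge.** The inputs are:

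- p, the share on oxygen at first dose: 30-50% (assumption).
- r, the time ratio on versus off oxygen: 2-3 (assumption).
- σ = 0.65 (Section 1.4, carried over from symptom resolution). The log-logistic form is also carried over, because the discharge paragraph does not restate a distribution.

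With B = p(1−p)(ln r)² and E = σ²π²/3 = 0.4225 × 3.290 = 1.390, the share of variance explained is R² = B/(B+E). The equivalent gain in children is 1/(1−R²) − 1 = B/E.

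| | B | R² | Gain in children | Interval narrower by 1−√(1−R²) |
|---|---|---|---|---|
| p = 0.3, r = 2 | 0.21 × 0.480 = 0.101 | 0.101/1.491 = 6.8% | 7% | 3% |
| p = 0.5, r = 3 | 0.25 × 1.207 = 0.302 | 0.302/1.692 = 17.8% | 22% | 9% |

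This takes 0.65 as the scale left after adjustment. If it is the unadjusted scale, R² = B/E, or 7-22%, and the gain is 8-28%. The smaller range is used here.

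**Does adjustment deliver this?** In the simulation, a covariate with R² of 0.10 or 0.20 cut the variance of the log time ratio by about 12% or 24%, with no material shift in its mean. A covariate with no prognostic value raised the variance by about 2%. On the Section 1.4 benchmark, with 0.65 as the unadjusted scale, high dose versus placebo power at one-sided 10% is 68.5% without the covariate, 70.2% at R² = 0.05 and 75.5% at R² = 0.20. This is a pairwise comparison, not the MCP-Mod test itself.

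**Clinically resolved status.** The formula above is for log time and does not carry over to a logistic model, so no size is given.

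**Time to end of oxygen.** Table 20 sets the time to 0 hours for children who need no oxygen after first dose. A log-logistic model works on log time, and ln 0 is undefined. If the zeros drop out, the fitted set is mainly children on oxygen, and baseline oxygen varies little. If they are kept by some substitution, baseline oxygen nearly separates zero from non-zero times. The ratio of 2-3 describes neither case, so the calculation does not apply to this endpoint.

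**The case against.** The strongest defence is that the related models adjust for the baseline value of their own outcome (summary score, viral load, RRS category), while time to discharge has no such value. Amendment 3 also revised the AFT covariates for the clinical course endpoints, so the list was reviewed. This weakens the charge of inconsistency for discharge. It carries less weight for clinically resolved status, whose symptom component has a baseline clinician score.

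Second, Section 5.3.2.3.2 also plans an AFT analysis of time to discharge on the baseline indicators, oxygen included. That softens the point but does not answer it: the analysis is exploratory, includes a treatment interaction, and does not supply the estimates for MCP-Mod.

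Third, the stakes are limited. None of these endpoints is in the Holm procedure of Section 5.2.3.2 or the interim decision rules of Section 5.6. This stands.

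A reader might go further in four ways that the document does not support:

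- That the unadjusted estimates are biased. Randomization keeps them valid.
- That chance imbalance in severity is a harm on top of wider intervals. It is already part of the unadjusted standard error.
- That baseline oxygen explains up to 36% of the variance, worth 57% more children. That needs σ = 0.4, which appears nowhere in the SAP, together with the most favourable oxygen share and ratio.
- That baseline oxygen dominates the end-of-oxygen model by a known amount. The 0-hour rule rules out that calculation.

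**Conclusion.** The omission is real in the main model for time to discharge and in the model for clinically resolved status. It costs precision in secondary and exploratory analyses and leaves the primary viral load test untouched. For discharge the loss is about 7-18% of log-time variance, or 7-22% more children, conditional on 30-50% on oxygen at first dose, a time ratio of 2-3 and a scale of 0.65 borrowed from symptom resolution. The SAP gives no prognostic strength for baseline severity, so the true figure could fall outside this range. No magnitude is claimed for clinically resolved status or for time to end of oxygen.

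**What to change.** Pre-specify one baseline severity term per model, taken from data before the first dose:

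- **Time to discharge:** baseline RRS category, or oxygen/feeding support yes/no. Use the same model for the estimates passed to MCP-Mod.
- **Clinically resolved status:** baseline RRS category or the baseline ClinRO key symptom score, not both, given the reduced stratum. Obtain the difference in proportions by standardization from the adjusted model, so that the reported quantity stays the same.
- **Time to end of oxygen:** first state how the 0-hour values enter the log-logistic model; the same covariate is reasonable after that.

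The cost is SAP wording and one or a few parameters per model, with no new data. If the covariate proves not prognostic, the variance rises by about 2%. Sparse RRS categories may need collapsing in the stratum with onset of 3 days or less; state that rule in advance. Make the change before the final unblinded results, since a covariate added afterwards would look data-driven.
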